for detecting significant lumen obstruction despite an average calcium score of greater than 1,000 (Latina J, et al, Radiology CV Imag 2021). The purpose of this investigation is to conclusively test the hypothesis that high-resolution CTA is not inferior to the current standard of cardiac catheterization for identifying significant CHD in patients with high-risk characteristics.

4. Study Procedures

[figure not shown]
a) Study design

The CORE-PRECISION MULTI-CENTER study is a prospective diagnostic accuracy study at three international sites comparing the diagnostic accuracy of UHR-CT to conventional, invasive coronary angiography by cardiac catheterization for the presence of hemodynamically significant CHD in 200 patients with high pretest probability of obstructive CHD. The enrollment at all centers is expected to commence in the summer of 2022: Johns Hopkins Hospital and Johns Hopkins Bayview Medical Center, Baltimore, USA, Iwate University Medical Center, Iwate, Japan, and Einstein Medical Center, Sao Paulo, Brazil. Sites will obtain approval from their local IRB and all patients will sign informed consent prior to participation. Each study site is expected to enroll participants, with the flexibility to enroll more if other sites experience slow recruitment.

Enrollment has been ongoing since November of 2019 at JHU as part of a pilot study using the same protocol with minor variations. For each participant, it is anticipated that the Screening Evaluation Periods will last less than 2 months and will be followed by the Imaging period (less than 60 days). All patients will be followed by additional 30 days after cardiac catheterization for occurrence of adverse events.

Screening-Evaluation Period

The screening period will begin when a patient is scheduled for a clinically indicated coronary angiogram. The protocol inclusion and exclusion criteria will be reviewed for each potential participant. Patients without history of CAD may enter an extended screening period that involves the first component of the CT imaging examination, namely the coronary calcium scan. If this scan shows a calcium score <400 , these patients will be considered late screen failures, will not proceed to contrast-enhanced coronary CT angiography, and will be

excluded from further participation in the trial. Patients with a calcium score of 400 or greater will proceed to coronary CT angiography and study participation.

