Patients will have one 18-20 gauge intravenous lines placed, preferably in an antecubital vein for contrast administration. The patient may be hydrated with normal saline intravenously (250 – 500 ml) prior to UHR-CT scanning, as per site practice. The patient will lie supine on the scanner table and be attached to a 3-lead system attached to the scanners monitoring system during scanning. Irregular heart rhythms will be noted and a full 12-lead ECG obtained if necessary to confirm cardiac rhythm. Patients may receive oral metoprolol and/or oral ivabradine 1-2 hours prior to the CT according to a hospital approved heart rate control algorithm. Goal for heart rate control is less than 60 bpm at the time of scan acquisition. Scout images for determining scanning range will be obtained in the anterior-posterior and lateral views. Patients with systolic blood pressure ≥ 100 will receive 0.4-1.2 mg sublingual nitroglycerin for vasodilation as per local practice. The adequate calcium score scan protocol will be confirmed on the scanner for each participant prior to the initiation of the calcium score scan. Patients will then be asked to hold their breath (approximately 10-15 seconds) and non-contrast CT imaging will be performed starting just cranial to the coronary ostia and extending just caudal to the apex of the heart in order to obtain a coronary calcium score. To limit radiation exposure, a coronary calcium score will only be generated for patients who

have not previously been stented as the presence of stents affects the accuracy of the calcium score. CT angiogram will then be performed to evaluate the coronaries using iodine contrast.

UHR-CT Protocol for Coronary Angiography

1) If the patient has not had prior stent placement or calcium scanning performed as part of the screening process, coronary calcium scan will be performed using the following protocol:

-No contrast.

-CT Imaging: tube voltage = 120kV, tube current = 150 mA, weight adjusted, gantry rotation speed = 0.230 seconds for half rotation, slice thickness = 3 x 4 mm, range = 144 mm. Estimated radiation dose = 0.5-2.0 mSv. Standard resolution mode.

2) Coronary angiography:

Coronary arterial imaging will be performed during a 4-6 ml/sec intravenous iodinated contrast infusion for a total volume of 60-120 ml. The automated bolus tracking feature will be used to judge contrast bolus arrival and optimize image quality.

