Not Applicable. No therapy will be given as part of research.

f) Definition of treatment failure or participant removal criteria

This study does not involve treatment. Subject removal will occur in the event that a participant experiences a previously unknown allergic reaction to iodinated contrast. Patients also may be removed if they are not able to follow instructions necessary to complete the study, or request withdrawal from the study.

g) Description of what happens to participants receiving therapy when study ends or if a participant's participation in the study ends prematurely.

No treatment will be given as part of research. If the participant's participation ends prematurely, there will be no impact on clinical care. Research information will be utilized as feasible.

5. Inclusion Exclusion Criteria

Inclusion Criteria

- A. Patients aged 45-85 years with history of CHD will be asked to participate. History of CHD is defined as history of coronary artery revascularization by percutaneous coronary intervention (PCI), stenosis of 50% or greater on prior angiogram (CTA or invasive), or a calcium score of 400 or greater. Women of child bearing potential must demonstrate a negative pregnancy test within 24 hours of the study CTA.

AND

- B. Suspected obstructive coronary artery stenosis based on clinical history and/or noninvasive testing, prompting a clinical referral for invasive coronary angiography; and/or planned PCI within the next 60 days.

AND

- C. Ability to understand and willingness to sign the Informed Consent Form.

Exclusion Criteria

- A. Known allergy to iodinated contrast media
- B. History of multiple myeloma or previous organ transplantation
- C. Renal failure (defined as estimated glomerular filtration rate [eGFR] < 60 ml/min/1.73m²) with the exception of patients with documented end stage renal disease on chronic dialysis who may participate
- D. Atrial fibrillation or uncontrolled tachyarrhythmia, or advanced atrioventricular block (second or third degree heart block) at the time of imaging.
- E. Evidence of severe symptomatic heart failure (NYHA Class III or IV) at the time of imaging;
- F. Known or suspected severe aortic stenosis
- G. Previous coronary artery bypass or other cardiac surgery
- H. Patients without history of CHD who had no or only mild coronary calcification on chest CT imaging within the past 5 years or had their most recent coronary calcium scan with a score < 400 .

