- I. . The presence of any other history or condition that the investigator feels would be problematic

6. Study Statistics

- a. Primary outcome variable**

The primary analysis will be a comparison of the diagnostic capability of the UHR-CT angiography to conventional coronary angiography at the patient level with the reference standard being quantitative flow reserve (QFR). A positive patient will be defined as having at least one vessel with a flow reserve <0.8 .

b. Secondary outcome variables

A secondary analysis will be performed at the vessel level. Similar to the primary analysis, a comparison of the diagnostic capability of UHR-CT angiography and conventional coronary angiography will be performed. A positive vessel will be defined as having at least stenosis with a flow reserve <0.8 . In addition, study groups will be compared for occurrence of adverse effects, radiation doses, contrast volume, and costs.

c. Statistical Plan including sample size justification and interim data analysis

In order to assess the diagnostic accuracy of UHR-CT angiography compared with invasive angiography to flow reserve we will consider the result from CT angiography as continuous measures on a patient, vessel, and segment level. The analysis will be based on the area under the receiver operating characteristic (ROC) curve (AUC). The gold standard will be coronary flow reserve estimations by either FFR, iFR, or QFR. Construction of the ROC curves using the CT and ICA measures will be based on the well-known result that the curve based on the risk score has the same ROC curve as the optimal curve based on the likelihood ratio (Pepe, 2003, Result 9.4). The risk score will be estimated by logistic regression analysis with CT angiography and ICA as independent predictor variables. The resulting risk score (the linear predictor from the logistic regression) will be used to construct the ROC curve. The AUC and its standard error will be estimated nonparametrically using standard methods (Pepe, 2003).

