Based on the literature (Rochitte et al, Eur Heart J 2014, Budoff et al, Jacc-Img 2015, Stuijzeand et al, JAMA Cardiol 2020) we are assuming an AUC of 0.83 for CT vs. 0.77 for ICA. Results will be compared using AUC analysis and 95% CI interval. We determined 6% as an acceptable noninferiority margin. For achieving 80% power with an alpha error of 5%, we require 180 patients. Given the complexity of the imaging protocol, we anticipate a 10% drop out rate which brings the **total required sample size to 200 patients.**

d. Early stopping rules

For any individual patient if an adverse reaction to intravenous contrast noted, if the clinical course changes or an intercurrent illness is noted in a patient; consideration will be given immediately for study withdrawal. There is no plan for early termination of study for efficacy.

However, a blinded interim analysis is planned after 12 months of enrollment to assess if enrollment goals should be adjusted to meet statistical requirements for executing the main outcome analysis. Enrollment may be shortened or extended accordingly.

8. Risks

a. Medical risks, listing all procedures, their major and minor risks and expected frequency.

CT Imaging

Risks of CTA imaging could include contrast related risks, radiation related risks, and symptoms of claustrophobia.

Contrast related: Patients may experience allergic reactions of CT contrast, even if previously unknown. These may include mild reactions (itching, hives, flushing, and nausea) to serious reactions including anaphylactic allergic reactions that can potentially lead to death. Medical personnel are always available to administer necessary medical care in the event of allergic reactions. Contrast may also cause contrast-induced nephropathy and renal damage. Hence patients with renal insufficiency are excluded from the study.

Radiation related: Short term risks of high doses of radiation (far higher than used in this study) include skin burns, gastrointestinal symptoms. Long-term risks of radiation include damage to cells and reduction in fertility. Women of childbearing age will have a lead apron placed over their abdomen and pelvis in order to reduce the radiation exposure to the ovaries. The estimated radiation dose for the entire cardiac computed protocol will be 4.8 mSv to 12.7 mSv depending on patient size and weight. A radiation dose of 10 mSv is commonly associated with a 0.1% increased risk of cancer (Einstein A, Circulation 2007).

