Patients with known allergic reactions to CT contrast or to iodine will be excluded from participation. At least 1 investigator (Physician) will be present during the study in the case of the need to treat a previously unknown contrast allergy and during saline infusion to monitor for adverse reactions. Patients with a reduced glomerular filtration rate (<60) or history of contrast induced nephropathy will be excluded. All patients will be required to have a minimum of 24 hours (recommended at least 48 hours) between their CTA scan and any other procedure requiring iodinated contrast administration, i.e., cardiac catheterization. All patients will have a creatinine repeated prior to their cardiac catheterization. A follow-up creatinine is strongly recommended within 72 hours after catheterization procedure. Patients will be hydrated with normal saline prior to and following their CTA scan. Menstruating women must have a negative pregnancy test within 24 hours of CTA and angiographic imaging. Pregnant women are excluded. Women of childbearing age will have a lead apron placed over their abdomen and pelvis in order to reduce the radiation exposure to the ovaries. Prospective scan triggering will be applied to all patients to reduce radiation dose compared to retrospective gating.

Intravenous catheters will be inserted by a nurse/technician who is well trained in that procedure.

All patients will be carefully screened for the presence of any contraindications prior to them signing the consent form.

It is recommended that nitroglycerin will **not** be administered to subjects who have used phosphodiesterase V inhibitors in the past 72h, i.e., treatment for erectile dysfunction. It is recommended that NSAIDS will be held prior to contrast media administration.

c. Plan for reporting adverse events unanticipated problems or study deviations.

Notification of events occurring within 30 days of study enrollment (CTA imaging) will be transmitted within 24 hours of occurrence electronically to the Study Coordinator and Johns Hopkins Hospital respectively. Safety monitoring of the study will be performed by the study team biannually. A data and safety monitoring board (DSMB) will be appointed for specifically monitoring the safety of participants and data. The DSMB will be outside JHU.

d. Legal risks such as the risks that would be associated with breach of confidentiality.

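### Sections 5 and 8 disagree on renal eligibility (dialysis and prior contrast nephropathy), and Sections 4 and 8b disagree on saline hydration around the study CTA

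*Combined protocol and SAP*

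**What the plan says.** **Eligibility.** Section 5, exclusion C, sets the renal threshold at an eGFR of 60 ml/min/1.73m², "with the exception of patients with documented end stage renal disease on chronic dialysis who may participate". Section 8a (CT Imaging, contrast-related risks) names nephropathy as a hazard and concludes: "Hence patients with renal insufficiency are excluded from the study". Section 8b states: "Patients with a reduced glomerular filtration rate (<60) or history of contrast induced nephropathy will be excluded". Neither part of Section 8 mentions dialysis. Section 5 does not name contrast nephropathy. The nearest criterion is exclusion I: "The presence of any other history or condition that the investigator feels would be problematic".

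**Screening.** The Screening-Evaluation Period text in Section 4 says: "The protocol inclusion and exclusion criteria will be reviewed for each potential participant". Section 8b adds: "All patients will be carefully screened for the presence of any contraindications prior to them signing the consent form". That sentence does not list the contraindications.

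**Hydration.** Section 4, UHR-CT Imaging: "The patient may be hydrated with normal saline intravenously", with 250 to 500 ml before scanning and according to site practice. Section 8b: "Patients will be hydrated with normal saline prior to and following their CTA scan".

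**Interval and creatinine.** For the gap between CT and catheterization, Section 4 recommends at least 24 to 48 hours; 8b requires 24 hours and recommends 48. For the creatinine after CTA and before catheterization, Section 4 says it should be obtained; 8b says all patients will have it.

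**The concern.** These texts decide who receives the study CTA contrast (60 to 120 ml, Section 4) ahead of the catheterization contrast, and with what protection. The protocol itself treats contrast nephropathy as a risk of the CTA and offers renal exclusion as the answer. The rules that carry out that answer should therefore read the same wherever they appear.

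As written, a site that screens from Section 5 and scans from Section 4 could enroll a dialysis patient, or one with prior contrast nephropathy and an eGFR of 60 or more, although 8b says both are excluded. It could also give no saline after the scan, or none at all. Three international sites each obtain their own IRB approval. An IRB that relies on the risk section would be told of a narrower population than Section 5 admits. The coordinating center is to assure compliance with the protocol, but it cannot classify an enrolled dialysis patient while two parts of that protocol give different answers.

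**Working it through.** No arithmetic underlies this point; the check is a side-by-side reading.

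| Item | Sections 4 and 5 | Section 8 | Type of difference |
|---|---|---|---|
| Chronic dialysis | 5C: may take part | 8a, 8b: excluded, no exception | Conflict |
| Prior contrast nephropathy | Named in 0 of the 8 exclusions A to H; discretionary under I | 8b: excluded | Omission from Section 5 |
| Saline | Section 4: optional, before CTA, site practice | 8b: given before and after CTA | Content and force |
| CT-to-catheterization interval | Section 4: at least 24 to 48 h recommended | 8b: 24 h required, 48 h recommended | Force only |
| Pre-catheterization creatinine | Section 4: should be obtained | 8b: all patients | Force only |

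1. *Dialysis.* End-stage renal disease falls within renal insufficiency, so a dialysis patient whom 5C admits is excluded by the wording of 8a, and by 8b if the GFR is below 60. The documents give no order of precedence between sections.

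2. *Prior contrast nephropathy.* A patient with this history and an eGFR of 60 or more is excluded by nothing in A to H on renal grounds. Criterion I can catch the patient, but only if the investigator judges the history problematic. In 8b the exclusion is not discretionary.

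3. *Hydration.* Section 4 contains no saline after the scan and leaves the pre-scan infusion to local practice. This is a difference in what is done, not only in how firmly it is stated.

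4. *Interval and creatinine.* The hours are the same in both places, and 8b covers all patients. Section 4's enrollment rule asks only that the CTA come before the angiogram, and it says the angiogram will not be delayed. A short gap is therefore foreseeable, but 8b still forbids it. The repeat creatinine is the only one scheduled between the two contrast doses. The creatinine after catheterization is advisory in both sections, so it is not a discrepancy.

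5. *Can a site satisfy every section?* Yes. 5C is permissive and Section 4's hydration is optional, so a site that follows 8b throughout breaches nothing. The problem arises only at a site that works from Sections 4 and 5 alone.

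6. *Size.* The documents give no frequency for dialysis or prior contrast nephropathy in this population. For scale only, each 1% of the planned sample is 0.01 × 200 = 2 patients.

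**The case against.** The strongest reply is that the sections belong to one protocol and can be read together. Exclusion C is the operative eligibility text and contains a specific, evidently deliberate exception; 8a and 8b restate the general rule, and a specific exception ordinarily governs. Prior contrast nephropathy is excluded in 8b, contraindications are screened before consent, and criterion I supplies a mechanism. The interval uses the same hours in both places, and *should* against *will* for the creatinine is thin.

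Much of this stands. The dialysis exception is probably intended, and the interval and creatinine items are minor.

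Three things remain. If Section 5 governs, then 8a and 8b misdescribe who is excluded, and 8b's nephropathy exclusion has no named criterion behind it. Criterion I turns a stated exclusion into a matter of judgment. The hydration difference is one of content and is not resolved by reading the sections together.

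A reader might infer that enrolling dialysis patients is in itself an unsafe error. The documents do not support that: 5C admits them expressly, and the defect is that 8a and 8b do not say so. A reader might also infer that sites cannot comply with the protocol, or that all the safeguards contradict each other. Neither follows, because following 8b satisfies every section and two of the three safeguards differ only in force.

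**Conclusion.** The point holds as a conflict between stated rules on renal eligibility and hydration, and it should be fixed. There is one eligibility conflict (dialysis), one eligibility omission (prior contrast nephropathy) and one substantive safeguard conflict (hydration). The interval and creatinine wording is a minor addition.

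The conclusion rests on the current text of Sections 4, 5, 8a and 8b and on the absence of any order of precedence among them. It does not rest on an estimate of how many patients are affected, which the documents do not allow.

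This is a matter of patient safety and eligibility wording. A reader might suppose that the eligibility ambiguity undermines the diagnostic comparison; nothing in the documents supports that, and neither the AUC analysis nor the sample size of 200 is affected.

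**What to change.** - **Section 5:** add a history of contrast-induced nephropathy as a named exclusion.
- **Sections 8a and 8b:** carry over the dialysis exception from 5C. Exempt chronic dialysis patients from the routine saline and repeat-creatinine rules, and manage them according to nephrology advice or local practice.
- **Section 4, hydration:** adopt 8b's rule, before and after CTA, for all other patients.
- **Section 4, interval and creatinine:** state the 24-hour minimum and the pre-catheterization creatinine as required (the creatinine subject to the dialysis exemption), keeping Section 4's existing creatinine timing. Do not perform the study CTA if catheterization is scheduled within the following 24 hours. If catheterization is brought forward for clinical reasons after the CTA, it goes ahead, and the short interval or missing creatinine is recorded as a deviation. This respects the commitment not to delay the clinical angiogram.

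The cost is a wording amendment submitted to each site's own IRB, since there is no central IRB, and possibly a few patients not enrolled because the CTA cannot be done early enough. The interval and creatinine are not new demands, because 8b already states them. The analysis and sample size do not change.

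The protocol is dated March 4, 2025. Enrollment was expected to start in summer 2022 and run 18 to 24 months, which would end by about summer 2024, but the protocol allows an extension and current status is not stated. If enrollment has closed, the remaining action is to state which text governed and to review enrolled patients for deviations.

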The purpose of this investigation is to test the hypothesis that ultra-high-resolution CTA is not inferior to the current standard of cardiac catheterization for identifying significant CHD in patients with high-risk characteristics, including severe coronary artery calcification and coronary stents.

To generate the study hypothesis, we propose to enroll 200 patients over 18-24 months. Patients referred for cardiac catheterization with known CHD or severe coronary calcification and suspected obstructive coronary artery stenosis will be included. All patients will undergo both cardiac catheterization and UHR-CT for determining significant CHD as defined by coronary functional assessment. The primary end point will be the diagnostic accuracy by area-under-curve (AUC) method for identifying patients with hemodynamically significant CHD.

2. Objectives

Primary Objective

The primary objective of this study is to test the hypothesis that noninvasive UHR-CT is not inferior to invasive coronary angiography by cardiac catheterization for identifying patients with hemodynamically significant CHD.

Secondary Objectives

Secondary objectives include testing the diagnostic accuracy of UHR-CT vs. cardiac catheterization on a vessel and segment-based analysis, and comparison of adverse events and radiation doses between the CT and conventional angiography groups.

Patient-Based Hypotheses

- 1) Diagnostic accuracy of UHR-CT using visual assessment of coronary artery disease is non-inferior to invasive, conventional coronary angiography for identifying patients with hemodynamically significant CHD defined by an QFR-value of <0.8 in at least one vessel of 2.0 mm or larger in diameter.
- 2) Diagnostic accuracy of UHR-CT using quantitative assessment of coronary artery disease is non-inferior to invasive, conventional coronary angiography for identifying patients with hemodynamically significant CHD defined by an FFR-value of <0.8 in at least one vessel of 2.0 mm or larger in diameter.
- 3) UHR-CT coronary angiography is associated with lower radiation dose than conventional, invasive coronary angiography.
- 4) UHR-CT coronary angiography is associated with lower adverse effects than conventional, invasive coronary angiography.

Vessel Based Hypotheses

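### The only ROC model in section 6c combines CT and ICA in one logistic score, so followed literally it does not give the CT-versus-ICA AUC difference that the non-inferiority test needs

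*Combined protocol and SAP*

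**What the plan says.** Three places in the combined protocol and SAP define the primary question as a contrast between two tests.

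- Section 2 (Primary Objective) sets the hypothesis that "noninvasive UHR-CT is not inferior to invasive coronary angiography by cardiac catheterization for identifying patients with hemodynamically significant CHD".
- Section 6a states: "The primary analysis will be a comparison of the diagnostic capability of the UHR-CT angiography to conventional coronary angiography at the patient level". The reference standard is QFR.
- The sample-size paragraph of section 6c assumes an AUC of 0.83 for CT and 0.77 for ICA, with a 6% margin, and adds: "Results will be compared using AUC analysis and 95% CI interval".

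The modelling paragraph of section 6c describes something else. It begins by referring to "Construction of the ROC curves using the CT and ICA measures". It then specifies one model, "The risk score will be estimated by logistic regression analysis with CT angiography and ICA as independent predictor variables", and one curve: "The resulting risk score (the linear predictor from the logistic regression) will be used to construct the ROC curve". Estimation follows: "The AUC and its standard error will be estimated nonparametrically using standard methods".

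The document does not describe a model or curve for CT alone or for ICA alone, an AUC difference, a standard error for that difference, or which confidence limit is set against the margin.

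**The concern.** The quantity to be tested is AUC(CT) minus AUC(ICA). A regression with both tests as predictors gives one score per patient and one AUC, which describes how well the two tests together predict a positive QFR. It is not the AUC of CT, and it is not a difference.

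The rationale given for the model makes the literal reading hard to dismiss. The cited result, that a risk score has the same ROC curve as the optimal likelihood-ratio rule, matters when several measures are combined. With one continuous predictor and a positive slope, the logistic score is only a monotone transform of that predictor. The empirical AUC is then unchanged and no regression is needed.

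An analyst who follows section 6c would therefore have either no contrast to report or a choice of contrast to make after seeing the data. This affects the single primary hypothesis of the study.

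**Working it through.** **1. The plan's own figure.** Inputs from section 6c: AUCs 0.83 and 0.77, margin 0.06, power 80%, alpha 5% (sidedness not stated), 180 evaluable patients, 10% dropout. The dropout step reproduces: 180 / 0.9 = 200. The 180 cannot be reproduced strictly, because the document gives neither the prevalence of QFR-positive patients nor the correlation r between the two AUC estimates. Both are assumed here.

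For a paired non-inferiority comparison of two AUCs:

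- Var(difference) = V1 + V2 - 2r√(V1·V2), with Hanley-McNeil variances.
- N is set so that (1.96 + 0.84) × SE ≤ 0.06 + (0.83 - 0.77) = 0.12, i.e. one-sided 0.025.

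| Prevalence | N at r = 0 | N at r = 0.7 |
|---|---|---|
| 0.3 | 300 | 92 |
| 0.5 | 214 | 67 |
| 0.7 | 209 | 66 |

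Prevalence 0.3 with r = 0.4 gives 181. The stated 180 is therefore compatible with a two-AUC contrast, which is further evidence that a contrast was intended.

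**2. What the joint model estimates.** Assume binormal scores with equal variances and within-class correlation ρ between the CT and ICA scores. The separation of each test is d = √2·Φ⁻¹(AUC):

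- CT: √2 × 0.954 = 1.349
- ICA: √2 × 0.739 = 1.045

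The best linear combination has D² = (d₁² + d₂² - 2ρd₁d₂) / (1 - ρ²), and its AUC is Φ(D/√2).

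- ρ = 0.3: D² = (1.821 + 1.092 - 0.846) / 0.91 = 2.271, D = 1.507, AUC = Φ(1.066) = 0.857
- ρ = 0.5: D² = (1.821 + 1.092 - 1.410) / 0.75 = 2.004, D = 1.415, AUC = Φ(1.001) = 0.842

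At ρ = 0.7 the combined AUC is 0.831, close to that of CT alone. The numerical gap thus depends on ρ and can be small, but in every case the result is one AUC and not a difference.

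**3. Why that AUC cannot be set against ICA.** Subtracting ICA's own squared separation gives D² - d₂² = (d₁ - ρd₂)² / (1 - ρ²), which is never negative. Under these assumptions the combined score is at least as accurate as ICA, however poor CT is.

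Take a CT that is worse by the full margin, 0.71 against 0.77. The combined AUC is still 0.793 at ρ = 0.3 and 0.779 at ρ = 0.5.

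As a hypothetical, 1,000 trials per setting were simulated with n = 180, prevalence 0.5, ρ of 0.3, 0.5 and 0.7, and a lower 95% limit required to exceed -0.06. With CT at 0.71, the joint score passed against ICA in 100% of trials. CT alone against ICA passed in 2.6% to 2.8%, close to the nominal 2.5%.

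**4. Effect of separate curves on power.** At N = 180, with the planned AUCs, one-sided 0.025 and Hanley-McNeil variances:

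| Prevalence | r = 0 | r = 0.3 | r = 0.5 | r = 0.7 |
|---|---|---|---|---|
| 0.5 | 0.73 | 0.87 | 0.95 | >0.99 |
| 0.3 | 0.58 | 0.74 | 0.86 | 0.98 |

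This is the contrast for which the 180 appears to have been set, so the correction does not of itself call for a new N.

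**The case against.** The strongest reply is that the model sentence is loose drafting. The sentence before it speaks of curves in the plural, section 6a calls for a comparison, and the sample-size paragraph gives two AUCs, a margin and a confidence interval. On that view each test is the predictor in its own model. The intention is clear and stands. It does not repair the text, because no sentence describes two models, and the score and the curve that follow are both singular.

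A reader might infer more than the documents support on four points:

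- **That the primary hypothesis will go untested.** The objective, margin and assumed AUCs are all stated. The conflict is between them and one modelling paragraph.
- **That the trial has a 100% false-pass rate.** The document never says the joint score will be compared with ICA. The figure is nearly a mathematical consequence of having ICA inside the score. It shows what one possible misuse would do and is not an error rate of this plan.
- **That ICA will be dichotomised and so lose AUC.** Section 6c says "we will consider the result from CT angiography as continuous measures on a patient, vessel, and segment level" and is silent on the scale of ICA. However, section 4 (Conventional Coronary Angiography) sends the angiograms for quantitative analysis, which points to a continuous measure. The silence needs a clarifying phrase and no more.
- **That an unpaired variance will be used.** The Abstract has every patient undergo both tests, and section 6c refers to standard nonparametric methods. Not naming a paired method is thin specification and does not show an unpaired analysis.

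Fitting and evaluating the score on the same patients matters only under the joint model. It disappears once each test has its own empirical curve.

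**Conclusion.** The point holds as a conflict within the plan. Section 6c gives one concrete rule, and followed literally that rule yields the AUC of CT and ICA combined, while sections 2 and 6a and the sample-size paragraph require a difference between two AUCs.

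At the planned values the combined AUC would be about 0.84 to 0.86, against 0.83 for CT and 0.77 for ICA. That size rests on binormal scores and a within-class correlation of 0.3 to 0.5, neither of which the document states. The structural conclusion needs neither assumption: one score containing both tests gives one AUC and no contrast. Were that score set against ICA, an inferior CT could not be detected.

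The design, the margin and the sample size are not put in question by this point. The paragraph should be corrected before the primary analysis is run, because it governs the only primary test and leaves the choice of contrast open.

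**What to change.** Replace the joint-model sentences in section 6c with the following specification:

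1. One empirical ROC curve and AUC from the CT measure alone, and one from the ICA measure alone. Both measures are continuous and summarised per patient by the same rule (for example, the worst stenosis in any vessel of 2.0 mm or larger).
2. The estimand AUC(CT) minus AUC(ICA), with a paired nonparametric confidence interval such as DeLong's.
3. The decision rule: non-inferiority is declared if the lower limit of the two-sided 95% interval is above -0.06. This also settles the sidedness, which is not stated at present.
4. Any logistic model containing both tests is labelled exploratory, as an analysis of incremental value, with correction for optimism.

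The per-patient summary and DeLong's method are suggestions; another rule applied equally to both tests, or another paired nonparametric interval, would serve. The cost is a change of SAP wording. No new data are needed, and the change does not itself alter the 180 evaluable or 200 enrolled patients.
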